9.1.9 Clinic Staff Follow-up Surveys (end of site data collection)

Following the end of recruitment at a site, all staff in practices who were assigned to the NRTS condition and who were involved in the FreSH trial will complete follow-up surveys. Surveys to be administered include:

- Organizational Readiness for Change (to be completed by the person at the clinic who will perform the study intervention)
- Feasibility of intervention measure
- Acceptability of intervention measure
- Appropriateness of intervention measure

9.1.10 Clinic staff interviews (end of site data collection)

10-12 dentists and 10-12 other staff from practices assigned to the NRTS condition will participate in a 60-minute phone interview conducted by Northwestern University Co-Investigators to gain information about future implementation of NRTS in dental practices. The interviews will focus on obtaining feedback about feasibility, acceptability, and implementation of NRTS. Participants will be paid \$50 for completing the interviews.

10 ASSESSMENT OF SAFETY

10.1 Specification of Safety Parameters

Safety monitoring for this study will focus on Unanticipated Problems (UPs) involving risks to participants, including unanticipated problems that meet the definition of a serious adverse event. In addition, adverse events (AEs) including SAEs will be recorded, and the PI will monitor these events to grade severity, relationship to the study intervention, and assess whether the nature, severity, or frequency is unexpected. Any time a participant spontaneously reports (calls the study or the practitioner) an AE including SAE or UP, it will be recorded. Practitioners will be trained to direct any participants reporting AEs to Hennepin Healthcare study staff and will alert study staff of any reports of AEs. Adverse events to study medication will be queried at the 1-, 3-, and 6-month follow-up assessments.

Safety events will be recorded and reported into the National Dental PBRN safety event reporting system maintained by the NCC if the events are determined to be both unexpected and related to the study intervention. Study PI [name], will be informed via the safety event system when events are reported.

10.1.1 Unanticipated Problems

The Office for Human Research Protections (OHRP) considers unanticipated problems involving risks to subjects or others to include, in general, any incident, experience, or outcome that meets **all** of the following criteria:

- unexpected in terms of nature, severity, or frequency given (a) the research procedures that are described in the protocol-related documents, such as the IRB-approved research protocol and informed consent document; and (b) the characteristics of the subject population being studied;
- related or possibly related to participation in the research (“possibly related” means there is a reasonable possibility that the incident, experience, or outcome may have been caused by the procedures involved in the research); and
- suggests that the research places subjects or others at a greater risk of harm (including physical, psychological, economic, or social harm) than was previously known or recognized.

10.1.2 Adverse Events

An adverse event is any untoward or unfavorable medical occurrence in a human subject, including any abnormal sign (for example, abnormal physical exam or

laboratory finding), symptom, or disease, temporally associated with the subject's participation in the research, whether or not considered related to the subject's participation in the research.

10.1.3 Serious Adverse Events

A serious adverse event (SAE) is one that meets one or more of the following criteria:

- Results in death
- Is life-threatening (places the subject at immediate risk of death from the event as it occurred)
- Results in inpatient hospitalization or prolongation of existing hospitalization
- Results in a persistent or significant disability or incapacity
- Results in a congenital anomaly or birth defect
- An important medical event that may not result in death, be life threatening, or require hospitalization may be considered an SAE when, based upon appropriate medical judgment, the event may jeopardize the subject and may require medical or surgical intervention to prevent one of the outcomes listed in this definition.

10.2 Time Period and Frequency for Event Assessment and Follow-Up

The PI will record all events with start dates occurring any time after informed consent is obtained until 7 (for non-serious AEs) or 30 days (for SAEs) after the last day of study participation. At each study visit, the investigator will inquire about the occurrence of AE/SAEs since the last visit. Events will be followed for outcome information until resolution or stabilization. We also instruct participants to contact study staff via phone if they have problems with the medication

10.3 Characteristics of an Adverse Event

Each event will be recorded on an appropriate case report form that includes assessment of the characteristics defined below. These characteristics, along with the frequency of an event's occurrence, will be considered in determining if the event is a UP.

10.3.1 Relationship to Study Intervention

To assess relationship of an event to study intervention the following guidelines are used:

1. Related (Possible, Probable, Definite)

- a. The event is known to occur with the study intervention, and/or
 - b. There is a temporal relationship between the intervention and event onset and/or
 - c. The event abates when the intervention is discontinued, and/or
 - d. The event reappears upon a re-challenge with the intervention.
2. Not Related (Unlikely, Not Related)
- a. There is no temporal relationship between the intervention and event onset, and/or
 - b. An alternate etiology has been established.

10.3.2 Expectedness

The Study PI and/or study-appointed, clinically/medically responsible individual will determine whether an AE is expected or unexpected. An AE will be considered unexpected if the nature, severity, or frequency of the event is not consistent with the risk information previously described for the intervention.

10.3.3 Severity of Event

The following scale will be used to grade adverse events:

1. Mild: no intervention required; no impact on activities of daily living (ADL)
2. Moderate: minimal, local, or non-invasive intervention indicated; moderate impact on ADL
3. Severe: significant symptoms requiring invasive intervention; subject seeks medical attention, needs major assistance with ADL

10.4 Reporting Procedures

10.4.1 Unanticipated Problem Reporting

Incidents or events that meet the OHRP criteria for unanticipated problems require the creation and completion of an unanticipated problem report form. OHRP recommends that investigators include the following information when reporting an adverse event, or any other incident, experience, or outcome as an unanticipated problem to the IRB:

- appropriate identifying information for the research protocol, such as the title, investigator's name, and the IRB project number;
- a detailed description of the adverse event, incident, experience, or outcome;

- an explanation of the basis for determining that the adverse event, incident, experience, or outcome represents an unanticipated problem;
- a description of any changes to the protocol or other corrective actions that have been taken or are proposed in response to the unanticipated problem.

To satisfy the requirement for prompt reporting, unanticipated problems will be reported using the following timeline:

- Unanticipated problems that are serious adverse events will be reported to the IRB within 1 week of the investigator becoming aware of the event.
- Any other unanticipated problem will be reported to the IRB within 2 weeks of the investigator becoming aware of the problem.
- All unanticipated problems should be reported to appropriate institutional officials (as required by an institution's written reporting procedures), the supporting agency head (or designee), and OHRP within one month of the IRB's receipt of the report of the problem from the investigator.

All unanticipated problems will be reported to NIDCR concurrently with reporting to the IRB. These reports will be made to NIDCR's centralized reporting system via Rho Product Safety:

- Product Safety Fax Line (US): [name]
- Product Safety Fax Line (International): [contact]
- Product Safety Email: [contact]

General questions about UP reporting can be directed to the Rho Product Safety Help Line (available 8:00AM – 5:00PM Eastern Time):

- US: [name]
- International: [contact]

10.4.2 Serious Adverse Event Reporting

Any AE meeting the specified Serious Adverse Event criteria will be submitted on an SAE form to NIDCR's centralized safety system via Rho Product Safety. This report may be sent by fax or email. Once submitted, Rho Product Safety will send a confirmation email to the investigator within 1 business day. The investigator should contact Rho Product Safety if this confirmation is not received. This process applies to both initial and follow-up SAE reports.

SAE Reporting Contact Information:

- Product Safety Fax Line (US): [name]
- Product Safety Fax Line (International): [contact]
- Product Safety Email: [contact]

General questions about SAE reporting can be directed to the Rho Product Safety Help Line (available 8:00AM – 5:00PM Eastern Time):

- US: [name]
- International: [contact]

All SAEs will be followed until resolution or stabilization.

11 STUDY OVERSIGHT

The principal investigator will be responsible for study oversight, including monitoring safety, ensuring that the study is conducted according to the protocol and ensuring data integrity. Study progress and safety will be reviewed monthly by the PI, when data will be reviewed for safety concerns and data trends. Reportable events that arise during the conduct of the study will be promptly submitted to the IRB. If necessary, additional steps may be taken to ensure data integrity and protocol compliance.

12 CLINICAL SITE MONITORING

NIDCR will determine whether clinical site monitoring is needed.

Node Coordinators will provide study training to practitioner sites. Remote monitoring activities will be conducted at the NCC and ARC Nodes to evaluate study processes and documentation based on NIDCR standards and principles of good clinical practice.

Remote monitoring activities will primarily involve quality management (QM) procedures to ensure completeness and accuracy of data collection. This study will follow the general guidelines for conducting monitoring for the network's clinical studies documented in Chapter 6 of the National Dental PBRN Network Operating Procedures. The NOP and all study-specific documentation will be stored on the HUB website and accessible to all study team members. The NIDCR reserves the right to conduct independent clinical site monitoring as necessary.

STATISTICAL CONSIDERATIONS

12.1 Study Hypotheses

Hypothesis 1 (primary): Participants receiving the NRTS intervention will have a higher frequency of biochemically confirmed abstinence at 6 months post enrollment compared to ET.

Hypothesis 2a: Participants receiving NRTS will be more likely to have a 24-hour quit attempt than ET.

Hypothesis 2b: Participants receiving NRTS will have greater reductions in smoking heaviness compared to baseline than ET.

Hypothesis 3a: Use of nicotine replacement therapy (patch and lozenge) will mediate the effect of NRTS on biochemically confirmed abstinence at 6 months post enrollment.

Hypothesis 3b: Perceptions of NRT safety and efficacy will mediate the effect of NRTS on biochemically confirmed abstinence at 6 months post enrollment.

Hypothesis 3c: Intention to use NRT will mediate the effect of NRTS on biochemically confirmed abstinence at 6 months post enrollment.

Hypothesis 3d: Intention to quit smoking will mediate the effect of NRTS on biochemically confirmed abstinence at 6 months post enrollment.

Hypothesis 4a: NRTS will be considered feasible to administer in dental settings.

Hypothesis 4b: NRTS will be acceptable to practitioners and patients.

Hypothesis 5: NRTS will be cost effective.

12.2 Sample Size Considerations

The primary outcome for the UH3 trial is biologically verified (via CO testing) 7-day point prevalence abstinence (PPA) from use of combusted tobacco at 6-months post-intervention, and the power calculations presented here pertain to this outcome only.

Calculations were done using a variety of assumptions for cluster size (the number of patients per cluster, which we assumed was fixed across clusters), the Intraclass Correlation Coefficient (ICC), the PPA in the ET group ($P_{\neg ET}$), and the PPA in the NRTS group ($P_{\neg NRTS}$). Specifically, we used ICCs of .01, .013, and .016; cluster sizes of 20, 22, and 24 (corresponding to total sample sizes 1000, 1100, and 1200); $P_{\neg ET}$ values of 4.5%, 5%, and 5.5%; and effect sizes ($P_{NRTS} - P_{ET}$) of 5%-7% in increments of 0.5%. The number of clusters was kept fixed at 50, and all calculations assumed a type 1 error of 5% and a two-sided test.

For the ICC, we observed a value of .013 in preliminary studies and assume that is the most likely ICC we will observe in our study. The P-ET range was based on the observed value of 4.7% in preliminary studies and further assumes CO will verify only 85% of self-report. We believe the effect size range represents achievable intervention effects, and brackets the effect size of 5.5% seen in a similar study.

The target cluster size of 24 was chosen to provide approximately 80% power to detect effect sizes of 5.0 percentage points or greater assuming an ICC of 0.013 and a rate in the ET arm of 5.5% (Table 11.1). Using the point estimates of 4.7% for ET and the effect size of 5.5% seen in a similar study would result in almost 90% power. With an ET rate of 5.5%, power increases to over 90% for effect sizes of 6 percentage points or more, and over 94% for effect sizes of 6.5 percentage points or larger.

Table 11.1. Power to detect given effect sizes

ICC	# clusters	cluster size	Total N	Power					
				Prob in ET arm	Diff in quit rate between NRTS and ET arms				
				5.0%	5.5%	6.0%	6.5%	7.0%	
0.010	50	24	1200	4.5%	86.8%	91.5%	94.7%	96.9%	98.2%
				5.0%	84.6%	89.8%	93.5%	96.0%	97.7%
				5.5%	82.4%	88.1%	92.2%	95.1%	97.1%
0.013	50	24	1200	4.5%	84.9%	90.0%	93.6%	96.1%	97.7%
				5.0%	82.6%	88.2%	92.2%	95.1%	97.0%
				5.5%	80.3%	86.3%	90.8%	94.1%	96.3%
0.016	50	24	1200	4.5%	83.0%	88.5%	92.4%	95.2%	97.1%
				5.0%	80.6%	86.5%	90.9%	94.1%	96.3%
				5.5%	78.3%	84.5%	89.3%	92.9%	95.4%

12.3 Final Analysis Plan

Demographics, baseline smoking history, and smoking behavior will be summarized across the aggregate sample and descriptively compared between clinics and treatment groups. Any large imbalances at the individual level will be considered for inclusion as a covariate. We will include the cluster-level stratification factors as covariates (minority race/ethnicity and payer mix). The distribution of each of the primary and secondary

study outcomes will be assessed using both parametric and graphical methods to determine the most appropriate modeling distribution (e.g., binomial, normal and zero-inflated distributions). Transformations of the outcome (e.g., log transform towards normality) will be considered if a model does not meet its assumptions. We will report point estimates (unstandardized effects size/magnitude) and associated 95% confidence intervals (precision). All hypotheses will be evaluated at a two-tailed alpha level of .05.

Sex and race as biological variables. We will test for effect modification by sex and race for the primary outcome. However, insofar as our proposal does not include hypotheses regarding sex and racial differences in treatment outcomes, we will conduct our hypothesis testing using both sexes and all races combined. This will be accomplished by adding a product term of group and sex or race (each will be evaluated separately) to the model. Given the low power for interaction effects, we will report the simple effects and associated confidence intervals both numerically and graphically to determine the nature of any effect modification.

[figure not shown]
To test hypothesis 1, we will compare treatment groups with respect to the primary outcome (biologically verified 7-day PPA from use of combusted tobacco at six months) using generalized hierarchical linear modeling⁴³⁻⁴⁵ with a binomial distribution and logit link (aka mixed effects logistic regression) that account for the clustering of individual observations within dental practice, while adjusting for various patient and practice related factors.^{46,47} The first level of the model (participant) will include any individual level covariates. The second level of the model will include the fixed effects for treatment group (ET=0, NRTS=1) and the cluster level stratification factors and a random effect for the participant level intercept. A significant coefficient for the treatment group indicator with an odds ratio > 1 would provide support for the effectiveness of NRTS on smoking abstinence at 6 months.

This same model framework will be used to examine the secondary outcomes of abstinence at 1 month and abstinence at 3 months and whether there was a quit attempt at 1,3, or 6 months. To determine whether the intervention had an effect on smoking heaviness over time, we will use a three-level hierarchical linear model that will account for the nesting of observations within persons and persons nested within practices. The first level of the model will include a categorical fixed effect for time (baseline [reference group], 1 month, 3 month, 6 month). The second level of the model will include fixed effect for any individual level covariates and random coefficient for the level 1 intercept. The third level will include for treatment group and the cluster level stratification factors and a random effect for the participant level intercept, including the terms for the time vectors representing the cross-level interactions. Significant terms for the cross-level interaction would indicate that the change in smoking heaviness differed

by treatment group, and will be followed up with examination and plots of the estimated marginal means do determine whether those in the NRTS group had greater decreases in smoking heaviness compared to the ET group.

We will test whether NRT utilization, perceptions of NRT effectiveness and safety, intent to use NRT, and intent to quit mediate the relationship between study group (ET vs NRTS) and smoking abstinence using a cross-lagged panel model (CLPM) in a structural equation modeling (SEM) framework.^{48,49} In a CLPM, the mediator and outcome at time t is regressed on arm, the mediator at $t-1$ and the outcome at $t-1$. Prior to estimating a final model, we will test for stationarity for the structural paths by comparing whether a model in which the paths are invariant fits significantly worse than one in which the paths are free to vary. We will also include the same set of covariates used in the primary analysis as time invariant covariates We will assess model fit using root mean square error of approximation (RMSEA) and the comparative fit index (CFI). Our criteria for good model fit will include an RMSEA of .08 or below⁵⁰ and a CFI of .95 or above.⁵¹ A significant indirect effect,⁵² based on bootstrapped standard errors,⁵³ would provide evidence for mediation.^{48,54} We will account for the clustering of participants within practices by including a random effect for the intercept terms in each path equation by employing the multilevel form of SEM (2-1-1-1 design).^{55,56} We will conduct separate models for each mediator.

Figure X. Cross lagged panel model for testing mediation. Covariates omitted for clarity.

Missing data. For all participants, we will attempt to gather follow-up information and reasons for dropout regardless of protocol completion and censor at the point of drop out. PBRN studies routinely attempt to collect reasons for dropout.⁵⁷ We anticipate

having about 11% attrition, as was found in previous work. We will compare baseline data between those with and without missing data and examine whether there are variables that are related to missingness. Analysis will use maximum likelihood (ML) approaches to produce estimates of the model parameters. One advantage of a ML approach when compared to other approaches such as multiple imputation, is that it makes use of all available data without requiring imputation of missing values, it is more efficient, and maintains congeniality between the missing data estimation and the analytical model.⁵⁸ ML estimates have been shown to be consistent when missing data is related only to covariates and observed values of the outcome.^{59,60}

To evaluate readiness for future implementation, we will conduct qualitative analyses of stakeholder interviews to gain insight into future implementation efforts. Using a structured debriefing form, post-interview notes will be written after each interview and reviewed by all Co-Is. Interviews will be professionally transcribed and deidentified. A qualitative expert will develop analytical codes using an iterative method in which interview notes are reviewed to: 1) consider whether the qualitative research agenda questions are appropriate and complete, 2) whether content saturation has been reached, and 3) develop an initial coding structure. Deductive codes will be drawn from the interview questions; inductive codes will capture concepts that emerge from the interviews. Once the coding scheme is developed, coders will independently code the transcripts and meet to resolve discrepancies. Final codes will be entered into NVivo qualitative data analysis software. A qualitative expert will conduct a framework matrix analysis⁶¹ to identify the most effective ways to organize the content and logistics of conducting the trial to help guide our trial protocol.^{61,62}

We will also report on descriptive statistics regarding the patient client satisfaction questionnaire, and the provider implementation measures.

Finally, we will conduct a cost effectiveness analysis (CEA). Our analyses will assess the incremental cost-per-quit and cost-per-quality adjusted life year (QALY) saved from a societal perspective and also a health system (e.g., accountable care organization) perspective in accordance with current practice recommendations.⁶³ The incremental cost-per-quit of NRTS vs. ET is estimated as: $(\text{Total costs at follow-up for NRTS participants} - \text{Total costs at follow-up for ET participants}) / (\text{Total successful quits at follow-up for NRTS participants} - \text{Total successful quits at follow-up for ET participants})$. The cost per QALY saved is estimated as $(\text{Total lifetime costs for NRTS participants} - \text{Total lifetime costs for ET participants}) / (\text{Total quality-adjusted life expectancy for NRTS participants} - \text{Total quality-adjusted life expectancy for ET participants})$.

The major direct costs for NRTS are described in the table below. Though some costs are incurred in both the NRTS and ET arms, we will measure them explicitly in the event that they do not entirely offset one another.

Cost data		
Cost	Basis for valuation	NRTS and/or ET
RX for Change AAR dental training	Value of time	NRTS & ET
AAR provided to smokers	Value of time	NRTS & ET
ADA Brochures	Purchase/photocopy/printing cost	NRTS & ET
NRT	National average NRT purchase price ¹⁶²	NRTS
Counseling on NRT use	Value of time	NRTS
Additional smoking cessation medications and services*	National average purchase price ¹⁶²	NRTS & ET

*Applies only to societal-perspective analyses

Personnel time will be valued at the national average wage for the relevant job type. The value of time for clinical personnel who may bill for their services will be based on a prorated fraction of a billing unit specific to the clinician type. We will track all participants' use of smoking cessation services (counseling, medication), whether provided as part of the intervention or not, to determine the net impact of the intervention on treatment use. This will allow us to determine whether the intervention in any way crowds out cessation efforts that would have occurred absent the intervention. We will make the conservative assumption that the provision of an electric toothbrush to participants randomized to ET does not in itself affect cessation and so we will ignore the cost of the toothbrushes. For the cost-per-quit analyses, costs from Table 1 will be assessed for each participant during the full course of follow-up. For the cost per QALY analyses, differences in future health care costs will be estimated based on existing literature.^{64–67}

Cessation outcomes for the cost-per-quit analyses will be based on the study's primary outcomes. Quality-adjusted life expectancy will be estimated based on CDC life table data adjusted for smoking status and weighted by health utility (quality adjustment) data from prior studies.^{68–71}

We will use Monte Carlo simulation methods which aggregate uncertainty in parameter estimates (e.g., 95% confidence bounds) and develop confidence bounds on our cost-per-quit estimates. Following standard methods of economic evaluation in prior studies, we will also perform parameter-specific sensitivity analyses in which individual parameters are varied singly and in combination, through plausible ranges to assess the relative impact different elements of the program have on overall cost-effectiveness.^{72–75}

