Objective	Brief Description/ Justification of Outcome Measure	Outcome Measured By	Time Frame

Assess the effectiveness of NRTS compared to ET on smoking heaviness
	
In addition to assessing the effectiveness of NRTS on abstinence, we want to assess the effect of NRTS on cessation-related behavior including reducing heaviness of smoking.
	
Smoking heaviness indicates cigarettes per day. Timeline follow-back measure of cigarettes per day on each of the past 7 days at 6-months post quit. We will measure cigarettes per day at baseline. We will then compute cigarettes per day at each follow-up timepoint by summing the number of cigarettes each person reports on each day of their follow-up survey and dividing by 7.
	
6 months following baseline.

Assess whether cessation medication utilization mediates the effectiveness of NRTS on 6-month abstinence.
	
Treatment utilization is one mechanism by which NRTS is hypothesized to have its effect.
	
Self-report survey items of use of the nicotine patch and nicotine lozenge at 1-, 3-, and 6- months post baseline. These items will be dichotomized as used NRT vs. hasn't used NRT in the 6 months post intervention. In addition, days of NRT use will be computed.
	
6-months following baseline.

Objective	Brief Description/ Justification of Outcome Measure	Outcome Measured By	Time Frame

Assess whether attitudes towards NRT (safety and efficacy) mediate the effectiveness of NRTS on 6-month abstinence.
	
We hypothesize that one mechanism of action of NRTS is to cause more favorable attitudes towards NRT.
	
Self-report survey items at baseline, 1-month, 3-month and 6-month surveys of perceptions of nicotine replacement therapy safety and efficacy. We will assess perceptions of NRT efficacy on a 5-point Likert-scale where higher scores indicate greater efficacy. We will assess safety with a single item measure on a 5-point Likert scale where higher scores indicate greater perceptions of NRT safety.
	
6-months following baseline.

Objective	Brief Description/ Justification of Outcome Measure	Outcome Measured By	Time Frame

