6.4 Treatment Assignment Procedures

This is a group randomized trial. All patients within a practice are assigned to the same condition. Practices will be instructed not to tell their patients to which condition the practice has been assigned until after the baseline survey is completed to prevent selection bias.

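### The smoking-heaviness model in Section 12.3 is valid but leaves baseline cigarettes per day unadjusted; a prespecified baseline-adjusted analysis would test Hypothesis 2b more precisely at little cost

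*Protocol*

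**What the plan says.** Section 4.2 makes smoking heaviness (cigarettes per day) a secondary outcome. Follow-up values are 7-day timeline follow-back averages, and the section adds that "We will measure cigarettes per day at baseline". Section 12.1 states Hypothesis 2b as "Participants receiving NRTS will have greater reductions in smoking heaviness compared to baseline than ET".

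Section 12.3 gives the model. Level 1 has a "categorical fixed effect for time (baseline [reference group], 1 month, 3 month, 6 month" set. On the arm, it says: "The third level will include for treatment group and the cluster level stratification factors and a random effect for the participant level intercept", then "including the terms for the time vectors representing the cross-level interactions". I read this as a fixed effect of treatment group, a practice-level random intercept and treatment-by-time interactions. The decision rule follows: "Significant terms for the cross-level interaction would indicate that the change in smoking heaviness differed" between the groups.

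On covariates, Section 12.3 fixes only the two stratification factors. For patient-level variables it says: "Any large imbalances at the individual level will be considered for inclusion as a covariate". Baseline cigarettes per day is not named as a covariate for this outcome.

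On allocation, Section 6.4 has practices withhold the arm from patients "until after the baseline survey is completed to prevent selection bias". Section 6.4.1 randomises a practice once its onboarding is complete, and under Section 6.3 its practitioners or staff then approach patients.

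**The concern.** With baseline as the reference time, the treatment-group coefficient is a freely estimated arm difference at baseline, and each interaction is the arm difference at that follow-up minus the arm difference at baseline. If the arms have the same expected baseline, that subtraction removes nothing systematic and only carries baseline noise into the effect. A model that conditions on baseline, or gives the arms one common baseline mean, then targets the same effect with a smaller variance.

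Hypothesis 2b rests on this contrast. Section 12.2 confines its power figures to abstinence, so nothing shows that heaviness has precision to spare. A real reduction in smoking could be reported with a wider interval than the data require. The only route to adjustment now is the large-imbalance rule, which would be applied after the baseline data have been compared by arm.

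**Working it through.** **Inputs from the protocol.** 50 practices, about 25 per arm; 24 patients per practice; two-sided alpha 0.05; ICC 0.013 (observed for abstinence); about 11% attrition.

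**Assumed, because the protocol is silent.** Correlation rho between baseline and follow-up cigarettes per day; ICC for cigarettes per day (0.013 borrowed, then varied); equal SDs over time (set to 1, then varied); normal outcomes; 80% power for the stated contrast as a reference point.

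**1. The plan's own figure.** None exists for heaviness. As a check of the cluster inputs, take the abstinence cell for 5.5% versus 10.5% at ICC 0.013. The design effect is 1 + 23 × 0.013 = 1.299, so effective n per arm is 600/1.299 = 461.9. The SE is √[(0.055 × 0.945 + 0.105 × 0.895)/461.9] = 0.01778, and power is Φ(0.05/0.01778 − 1.96) = 80.3%, as in Table 11.1.

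**2. Variance of the stated contrast.** With complete data and random intercepts, the 6-month interaction is the difference in mean change. The practice and person intercepts cancel, leaving 4(1 − rho)/600. At rho 0.5 this is 2/600, SE 0.0577.

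**3. Variance with baseline used.** The correlation between a practice's baseline and 6-month means is

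r = (rho + 23 × ICC)/(1 + 23 × ICC).

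The ratio of adjusted to unadjusted variance is (1 + r)/2. At rho 0.5 and ICC 0.013, r = 0.799/1.299 = 0.615 and the ratio is 0.808 (SE 0.0519). A full generalised least squares calculation with all four time points gives the same ratios.

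**4. Power.** If the stated contrast has 80% power, the adjusted one has Φ(2.802/√ratio − 1.96).

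| rho | ICC | variance ratio | variance cut | 80% becomes |
|---|---|---|---|---|
| 0.3 | 0.013 | 0.731 | 27% | 90.6% |
| 0.5 | 0.013 | 0.808 | 19% | 87.6% |
| 0.7 | 0.013 | 0.885 | 12% | 84.6% |
| 0.8 | 0.013 | 0.923 | 8% | 83.0% |
| 0.5 | 0.05 | 0.884 | 12% | 84.6% |
| 0.7 | 0.05 | 0.930 | 7% | 82.8% |

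With 21 patients per practice, to reflect attrition, the ratios at ICC 0.013 are 0.802 (rho 0.5) and 0.881 (rho 0.7). A simulation of 4,000 trials (rho 0.5, ICC 0.013, effect 0.165 SD, practice means) gave power of 79.9% for change and 86.8% for the adjusted analysis, with type I error of 5.0% and 4.8%.

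**5. Unequal SDs.** Section 9.1.2 lists baseline cigarettes per day among smoking-history items, while follow-up uses timeline follow-back, so equal SDs are not assured. Ignoring clustering, the ratio is (1 − rho²)/(k² + 1 − 2·rho·k), with k the baseline SD over the follow-up SD. For k = 1.25 it is 0.57 (rho 0.5) and 0.63 (rho 0.7); for k = 0.8 it is 0.89 and 0.98.

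**6. If recruitment shifts baseline.** Take a shift of 0.1 SD between arms.
- A stable shift, present at every time point: the change contrast is unbiased. A patient-level covariate removes only rho of the shift, so the bias is 0.1 × (1 − 0.5) = 0.05 SD at rho 0.5 and 0.03 SD at rho 0.7. Simulation with a true effect of −0.10 gave −0.05 and −0.07.
- A shift from selection on the baseline value itself, which regresses to the mean: the change contrast is biased by 0.1 × (1 − rho), or 0.05 SD at rho 0.5, and the adjusted estimate is unbiased.

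**The case against.** The strongest objection concerns recruitment. A reader might infer from Section 6.4 that the plan itself expects equal baseline means, so that a free baseline difference has no purpose. The documents do not support that. Section 6.4 conceals the arm from patients only. Practices are randomised first, and staff who know the arm then choose whom to approach; Section 9.1.8 even has staff at NRTS sites complete baseline surveys before training. Section 12.3 expressly provides for imbalances. A free baseline difference is thus a defensible safeguard. Under a stable 0.1 SD shift, the adjusted test's type I error would rise to about 16% at rho 0.5 (bias 0.05 over SE 0.0525) or about 11% at rho 0.7. A stable shift of roughly 0.05 SD is enough to cancel its advantage in mean squared error.

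This stands as a reason not to rely on the adjusted analysis alone. It does not favour the change contrast alone, which is the biased one if the imbalance regresses to the mean. The protocol gives no ground for preferring either pattern, or for the size of any shift.

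A reader might also infer that the change contrast was chosen without reason. It was not: Hypothesis 2b is worded as reduction from baseline, and the model follows it. That wording does not rule out adjustment, however, since regressing change on arm and baseline gives the same treatment coefficient as regressing the follow-up value on them.

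Finally, the size of the gain does not come from the documents, and Section 12.3 keeps the outcome distribution open, so the normal-theory figures are illustrative. That is right, and it limits how strongly the point can be put.

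**Conclusion.** The point holds as a matter of efficiency. The stated model is a standard, valid analysis, consistent with Hypothesis 2b and with correct type I error when there is no selection. It would be wrong to call it an error or a source of bias. It does leave unused a baseline measurement the trial already has, and under equal expected baselines that costs precision.

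The cost is modest and cannot be fixed from the protocol. At ICC 0.013 and equal SDs it is 27% of the variance at rho 0.3 and 8% at rho 0.8, equivalent to 80% power instead of about 91% or 83%. It shrinks further with a higher ICC or rho and depends on the ratio of baseline to follow-up SD. The point concerns one secondary outcome and does not touch the primary abstinence analysis. It is worth acting on because the change is cheap and would replace a decision made after seeing the imbalances.

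**What to change.** In Section 12.3, prespecify for smoking heaviness either of these:
- a model of the 1-, 3- and 6-month values with baseline cigarettes per day as a patient-level covariate, plus its practice mean; or
- a constrained-baseline model, in which the arms share one baseline mean and the treatment-by-time terms are the arm differences at each follow-up.

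Keep the currently stated unconstrained change contrast as a prespecified sensitivity analysis, report both estimates with their confidence intervals, and say that any disagreement will be reported as possible recruitment imbalance.

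The cost is a few sentences and one further model fit, with no new data. The downside is the possible bias of the adjusted estimate under a stable recruitment imbalance, which is why the two analyses should be reported together.
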